12.1. STUDY DRUG DOSAGE AND ADMINISTRATION

The study drug dosage groups are defined based on the preclinical and clinical experience with CimetrA.

Arms 1 and 2 doses were defined based on the preclinical data, presented in the Investigator Brochure, when CimetrA formulation demonstrated an anti-inflammatory activity in lower dosages. The rationale of additional dosage is based on the potential ability of CimetrA to be active in different ways in prevention of deterioration of COVID-19 patients. As per FDA's requirement for the dose finding, additional study arm dosage was defined based on the preclinical studies described above.

Minor dose adjustment was performed according to the CMC limitation as a result of the nano-particles characteristics.

Arm 1: CimetrA-1, with a total dose containing a combination of Curcuma longa rhizome dry extract 28 mg, Boswellia serrata resin dry extract 60 mg in spray administration – divided in 4 separate doses given as an add on therapy, total of 4 doses over 48 hours (day 1 and day 2), twice a day (morning and evening).

Single dose: 1ml of dose contain Curcuma longa rhizome dry extract 7 mg/ml, Boswellia serrata resin dry extract 15 mg/ml in spray administration , for one dose are required 5 puffs from the study drug spray.

Daily dosage is 2 ml which equal to 10 puffs from the study drug spray.

Arm 2: CimetrA-2, with a total dose containing a combination of Curcuma longa rhizome dry extract 19.6 mg, Boswellia serrata resin dry extract 42 mg in spray administration – divided in 4 separate doses given as an add on therapy, total of 4 doses over 48 hours (day 1 and day 2), twice a day (morning and evening).

	MGC Pharma Clinical Study Protocol	Protocol No.: MGC-009
		Version 02, 05 Sep 2021
		Page 50 of 76
A Phase IIb, double blind, placebo-controlled clinical study designed to evaluate the effect of CimetrA in patients diagnosed with COVID-19		CONFIDENTIAL

Single dose: 0.7 ml of dose contain Curcuma longa rhizome dry extract 4.9 mg/ml, Boswellia serrata resin dry extract 10.5 mg/ml in spray administration, for one dose are required 5 puffs from the study drug spray.

Daily dosage is 1.4 ml which equal to 10 puffs from the study drug spray.

Arm 3: Placebo, composed of the same solvent but without active ingredients, given as an add on therapy in spray administration, total of 4 doses over 48 hours (day 1 and day 2), twice a day (morning and evening).

Patients will be randomized in 1:1:1 ratio to one of the three arms.

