12.2. Packaging and Labelling of Study Products

CimetrA-1, CimetrA-2 and Placebo is supplied in a bottle containing 5 ml.

The Product is packed in a bottles with a spray pump. It is administered by spraying into the oral cavity.

bottles are closed with a validated spray delivery system , Spray pump on product bottle enables dosing 0.2 ml of CimetrA-1 /0.14 ml of CimetrA-2 in each press and will be packaged and labelled in compliance with the GMP, and EU regulation regarding drugs used in clinical trials.

The lot number and date of manufacture for the clinical lot used in the study will be provided to the clinical site and will be reported in the Clinical Study Report. The documentation supplied by the Sponsor for the study medication (i.e. Certificate of

	MGC Pharma Clinical Study Protocol	Protocol No.: MGC-009
		Version 02, 05 Sep 2021
		Page 51 of 76
A Phase IIb, double blind, placebo-controlled clinical study designed to evaluate the effect of CimetrA in patients diagnosed with COVID-19		CONFIDENTIAL

Analysis for the test product) will make it possible to retrace the composition and pharmaceutical profiles of the test product .

Study Product will be labeled with :

- Product name
- Dose
- Lot number
- Date of manufacture
- Protocol number
- Sponsor's name
- Instructions for use and storage
- "Investigational Use Only" statement

Placebo will be administrated in the same way, and will be identical in its characteristics to the study drug in order to prevent bias.

12.3. **Storage, Dispensing and Return of the Investigational product**

Bottles containing the study product should be stored at room temperature. Records should also be kept by the Investigator or pharmacist as to how much study drug was used by each subject. The study monitors must check during each visit the study drug supplied to ensure expiry date and sufficient amount of study drug. All investigational products must be kept in a locked area with access to the study drug limited to designated study personnel. Only personnel under the supervision of either the Investigator or the local pharmacist are authorized to dispense study drug. During storage at the pharmacy, the temperature will be monitored and recorded by a pharmacist or a temperature log. The Sponsor will be notified for any deviation from the storage conditions.

	MGC Pharma Clinical Study Protocol	Protocol No.: MGC-009
		Version 02, 05 Sep 2021
		Page 52 of 76

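### Arm 2 (CimetrA-2): the stated concentration and volume give 30% less of both extracts than the stated total dose

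*Protocol*

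**What the plan says.** Section 12.1 defines Arm 2 in two adjacent statements of the same entry.

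- The total: CimetrA-2 is given "with a total dose containing a combination of Curcuma longa rhizome dry extract 19.6 mg, Boswellia serrata resin dry extract 42 mg", and this is "divided in 4 separate doses given as an add on therapy, total of 4 doses over 48 hours (day 1 and day 2"). The synopsis repeats both totals.
- The single dose: "Single dose: 0.7 ml of dose contain Curcuma longa rhizome dry extract 4.9 mg/ml, Boswellia serrata resin dry extract 10.5 mg/ml in spray administration", delivered as 5 puffs, with a daily volume of 1.4 ml in 10 puffs.

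Section 12.2 adds the pump volume: "Spray pump on product bottle enables dosing 0.2 ml of CimetrA-1 /0.14 ml of CimetrA-2 in each press".

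For Arm 1, section 12.1 gives a total of 28 mg and 60 mg in four doses, each of 1 ml at 7 mg/ml and 15 mg/ml.

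**The concern.** For a liquid given by volume, the number of doses times the volume times the concentration must equal the total dose. For Arm 2 it does not, so the protocol gives two different amounts of active extract for one of its two active arms.

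Four uses of the dose are at stake:

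- **Dose contrast.** Section 12.1 says the additional dosage arm was set up to meet a regulatory dose-finding requirement. The ratio of the two active doses is then part of what the trial reports.
- **Label.** Section 12.2 lists the dose among the label items, and section 12.1 is the place that gives the strength.
- **Compliance.** Section 12.4 assesses it by volume. Turning volume into milligrams needs the concentration.
- **Pharmacokinetics.** Section 17 (PK test) lists dose-normalised Cmax and AUC, and also CL/F and Vz/F. All of these take the dose as an input.

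**Working it through.** **Inputs**

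| Quantity | Arm 1 | Arm 2 | Source |
|---|---|---|---|
| Volume per press | 0.2 ml | 0.14 ml | 12.2 |
| Puffs per dose | 5 | 5 | 12.1 |
| Stated volume per dose | 1 ml | 0.7 ml | 12.1 |
| Stated daily volume (10 puffs) | 2 ml | 1.4 ml | 12.1 |
| Curcuma concentration | 7 mg/ml | 4.9 mg/ml | 12.1 |
| Boswellia concentration | 15 mg/ml | 10.5 mg/ml | 12.1 |
| Number of doses | 4 | 4 | 12.1, synopsis |
| Stated total, Curcuma | 28 mg | 19.6 mg | 12.1, synopsis |
| Stated total, Boswellia | 60 mg | 42 mg | 12.1, synopsis |

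**Step 1: the volume is consistent.** Arm 1: 5 × 0.2 = 1 ml per dose and 10 × 0.2 = 2 ml per day. Arm 2: 5 × 0.14 = 0.7 ml per dose and 10 × 0.14 = 1.4 ml per day. All agree with the text.

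**Step 2: Arm 1 reproduces.** Total = doses × volume × concentration.

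- Curcuma: 4 × 1 × 7 = 28 mg, as stated.
- Boswellia: 4 × 1 × 15 = 60 mg, as stated.

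**Step 3: Arm 2 does not.**

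- Curcuma: 0.7 × 4.9 = 3.43 mg per dose; × 4 = 13.72 mg, against 19.6 mg stated. 13.72 / 19.6 = 0.70.
- Boswellia: 0.7 × 10.5 = 7.35 mg per dose; × 4 = 29.4 mg, against 42 mg stated. 29.4 / 42 = 0.70.

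**Step 4: what each statement implies.**

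| | From the stated totals | From the stated concentration and volume |
|---|---|---|
| Curcuma per dose | 19.6 / 4 = 4.9 mg | 3.43 mg |
| Boswellia per dose | 42 / 4 = 10.5 mg | 7.35 mg |
| Concentration, Curcuma | 4.9 / 0.7 = 7 mg/ml | 4.9 mg/ml |
| Concentration, Boswellia | 10.5 / 0.7 = 15 mg/ml | 10.5 mg/ml |
| Arm 2 / Arm 1, Curcuma | 19.6 / 28 = 0.70 | 13.72 / 28 = 0.49 |
| Arm 2 / Arm 1, Boswellia | 42 / 60 = 0.70 | 29.4 / 60 = 0.49 |

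The two columns describe different products. The first is a liquid of Arm 1 strength from a smaller pump. The second is a weaker liquid from the same smaller pump. Either is physically possible, and the four-dose volume of 4 × 0.7 = 2.8 ml fits the 5 ml bottle in both cases.

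**Step 5: effect on PK.** The two per-dose figures differ by 4.9 / 3.43 = 10.5 / 7.35 = 1.43. Any parameter that divides by dose (Cmax/dose, AUC/dose) or multiplies by it (CL/F, Vz/F) is off by that factor for Arm 2 if the figure used is not the one that matches the product.

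**The case against.** The strongest reply is that this is only a slip in units. The shortfall factor of 0.70 equals the 0.7 ml volume for both extracts, and 4 × 4.9 = 19.6 and 4 × 10.5 = 42 exactly. That pattern would arise if milligrams per dose had been written as mg/ml. It is a plausible cause, but the protocol does not say so and gives no other Arm 2 concentration. Section 12.1 mentions a minor dose adjustment for manufacturing reasons, which does not reconcile the figures. A reader cannot settle the matter from the document.

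Other points limit the consequences, and they stand:

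- The total is given identically in two places and the volume agrees throughout. The Arm 2 dose is inconsistently stated rather than absent.
- The written mismatch does not show that any patient would receive less drug than intended.
- The primary analysis in section 17 is an ANOVA across the three arms. It uses arm membership, not milligrams, and the protocol specifies no dose-response model. The primary test is unaffected; what suffers is the interpretation of the contrast between the active arms.
- PK sampling covers only 14 consenting patients, in Brazil and South Africa, and the parameters are to be estimated only where possible. Cmax, tmax and AUC without normalisation do not use the dose.
- Section 12.2 provides for a Certificate of Analysis, so the actual composition should be traceable.

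None of this removes the contradiction.

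**Conclusion.** The concern holds. Taken as written, the Arm 2 concentration and volume give 13.72 mg and 29.4 mg over the course, exactly 30% below the stated 19.6 mg and 42 mg. Arm 2 is therefore 70% of Arm 1 by the totals and 49% by the single-dose line. The result needs no assumption beyond reading the printed units literally, and the exact agreement for Arm 1 shows that the method is the one the protocol itself uses. The factor of 1.43 in the dose-dependent PK parameters is conditional: it arises only if the figure chosen does not match the product supplied. No view is taken on which Arm 2 figure is correct.

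This must be fixed, because the strength of an active arm in a trial that includes dose finding cannot be left with two values.

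**What to change.** The sponsor should check the Arm 2 total dose, concentration and volume per dose against the product release specification and the manufacturing record, and confirm which set describes the product supplied. The volume per press already agrees with the volume per dose and needs only to be confirmed alongside them. One consistent set should then be carried into the synopsis, sections 12.1 and 12.2, the label, the conversion of volume to milligrams for compliance, and the dose used for the PK parameters in section 17. It would help to give both milligrams per dose and mg/ml for each arm, clearly labelled, so that the arithmetic can be checked on the page.

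The cost is one check of existing records and a wording correction. The design, sample size and primary analysis do not change.

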12.2. Packaging and Labelling of Study Products

CimetrA-1, CimetrA-2 and Placebo is supplied in a bottle containing 5 ml.

The Product is packed in a bottles with a spray pump. It is administered by spraying into the oral cavity.

bottles are closed with a validated spray delivery system , Spray pump on product bottle enables dosing 0.2 ml of CimetrA-1 /0.14 ml of CimetrA-2 in each press and will be packaged and labelled in compliance with the GMP, and EU regulation regarding drugs used in clinical trials.

The lot number and date of manufacture for the clinical lot used in the study will be provided to the clinical site and will be reported in the Clinical Study Report. The documentation supplied by the Sponsor for the study medication (i.e. Certificate of

	MGC Pharma Clinical Study Protocol	Protocol No.: MGC-009
		Version 02, 05 Sep 2021
		Page 51 of 76
A Phase IIb, double blind, placebo-controlled clinical study designed to evaluate the effect of CimetrA in patients diagnosed with COVID-19		CONFIDENTIAL

Analysis for the test product) will make it possible to retrace the composition and pharmaceutical profiles of the test product .

Study Product will be labeled with :

- Product name
- Dose
- Lot number
- Date of manufacture
- Protocol number
- Sponsor's name
- Instructions for use and storage
- "Investigational Use Only" statement

Placebo will be administrated in the same way, and will be identical in its characteristics to the study drug in order to prevent bias.

12.3. **Storage, Dispensing and Return of the Investigational product**

Bottles containing the study product should be stored at room temperature. Records should also be kept by the Investigator or pharmacist as to how much study drug was used by each subject. The study monitors must check during each visit the study drug supplied to ensure expiry date and sufficient amount of study drug. All investigational products must be kept in a locked area with access to the study drug limited to designated study personnel. Only personnel under the supervision of either the Investigator or the local pharmacist are authorized to dispense study drug. During storage at the pharmacy, the temperature will be monitored and recorded by a pharmacist or a temperature log. The Sponsor will be notified for any deviation from the storage conditions.

	MGC Pharma Clinical Study Protocol	Protocol No.: MGC-009
		Version 02, 05 Sep 2021
		Page 52 of 76
A Phase IIb, double blind, placebo-controlled clinical study designed to evaluate the effect of CimetrA in patients diagnosed with COVID-19		CONFIDENTIAL

12.4. **Accountability and Compliance**

Each delivery must be acknowledged by the pharmacist (or authorized study team member responsible for the investigational medicinal product) by filling in the receipt record form. The study staff will confirm the receipt of clinical supply and will return signed drug accountability logs to the study monitor.

The pharmacist (or authorized study team member responsible for the investigational medicinal product) are responsible for ensuring the supervision of the storage and allocation of these supplies, which will be forwarded to the Investigator at the appropriate time before administration. The Investigator or pharmacist may dispense investigational drug only to subjects enrolled in the study. Treatment compliance will be assessed at all visits during the Treatment Period. It will be based on drug accountability (volume measure), and subject's diary review. Study drug compliance may be enhanced with regular telephone and other reminders. Drug accountability records must be maintained by the clinical investigation site at all times. At the last study visit, all used and unused investigational drug will be assessed for accountability by the study monitor. The subject identification number, the date, batch number/pack number, and quantity of study drug used by the subject will be checked for correctness and recorded on the appropriate accountability forms. Unused drug supplies will be returned to the Sponsor. At the end of the study, all the clinical supply and the corresponding accountability forms must be returned by the study monitor for reconciliation and destruction. A copy of these records must be kept at the clinical investigation site.

The inventory will be made available to the study monitor who will verify accountability and verify dose during the course of the study. Study drug orders, records of study drug receipts, dispensing records, and inventory forms located at

	MGC Pharma Clinical Study Protocol	Protocol No.: MGC-009
		Version 02, 05 Sep 2021
		Page 53 of 76
A Phase IIb, double blind, placebo-controlled clinical study designed to evaluate the effect of Cimetra in patients diagnosed with COVID-19		CONFIDENTIAL

the site will be examined and reconciled by the study monitor periodically during and at the end of the study.

13. **CONCOMITANT MEDICATIONS DURING THE STUDY**

13.1. **General guidelines**

All prior treatments received by the subject within 60 days of the initial screening visit will be recorded on the subject's CRF including the treatment's name, indication and the start and stop dates.

All concomitant medications taken by the subject (including prescription, over-the-counter, herbal supplements and health store products) must be recorded on the CRF, along with the indication and start and stop dates as well as daily dose.

13.2. **Allowed Concomitant Medications/Therapies during Study**

Concomitant medications allowed to be used in this study are those used at screening to control existing medical condition and/or those taken during the study to treat possible adverse events. All concomitant medications used to treat adverse events will be recorded in the subject's medical file and on the appropriate CRF page.

If intake of a drug should become necessary for any reason during the course of the study, the subject is required to inform the Investigator immediately, who will record the drug, the dose and the time of administration in the subject's CRF.

Standard of care treatment acceptable to be used while patient participates in study :

Treatment will include:

Supportive care - symptomatic

Painkillers

Anticoagulant therapy

Steroids

	MGC Pharma Clinical Study Protocol	Protocol No.: MGC-009
		Version 02, 05 Sep 2021
		Page 54 of 76
A Phase IIb, double blind, placebo-controlled clinical study designed to evaluate the effect of CimetrA in patients diagnosed with COVID-19		CONFIDENTIAL

REMEDSIVIR - Compassionate treatment

Antibiotic treatment as needed

Inhalations if necessary

Oxygen

The treatments offered above are given according to the guidelines of the Ministry of Health.

The treatment will be given to the patient according to the clinical judgment of the medical staff and in accordance with the patient's health condition, and therefore the treatment does not have to be the same in each of the medical centers participating in the study.

13.3. **Potential Adverse Events and risks for the patient in the study**

During Phase II study on 50 COVID-19 patients no drug related adverse events were reported. The full safety profile is presented above .

It is important to say that both active ingredients of the study drug is defined as GRAS and found to be safe with no adverse events in clinical studies. Based on the literature, the following data regarding the potential risks of the Curcumin and Boswellia is available –

1. Madhu K at al., Rahmani et al. and Selvi et al. reported gastrointestinal adverse events related to diarrhea, nausea and abdominal pain
2. Chuengsamarn et al. reported hot flashes and constipation that were observed in the clinical trial in type 2 diabetes patients .

14. **ADVERSE EVENT**

14.1. **Definition of adverse event**

Adverse event means any untoward medical occurrence associated with the use of a drug in

	MGC Pharma Clinical Study Protocol	Protocol No.: MGC-009
		Version 02, 05 Sep 2021
		Page 55 of 76
A Phase IIb, double blind, placebo-controlled clinical study designed to evaluate the effect of Cimetra in patients diagnosed with COVID-19		CONFIDENTIAL

humans, whether or not considered drug related.

An Adverse Event (AE) is any untoward medical occurrence in a subject administered a pharmaceutical product, whether it is related to the pharmaceutical product in question or not. This includes a change in a subject's condition or laboratory results, which has or could have a deleterious effect on the subject's health or well-being.'

In this study, local reactions due to study treatment will be captured in the diary, and this information will not be duplicated in the CRFs.

AEs to be recorded in the CRFs are systemic reactions that also are captured in the diary and other AEs occurring that are not due to study treatment.

14.2. **Methods for eliciting AEs**

All subjects should be carefully monitored for occurrence of AEs during the study and for a reasonable time period thereafter. No distinction should be made between the investigational treatment and the placebo treatment for the purpose of AE reporting.

All directly observed and spontaneously reported AEs should be recorded in the CRF. If no AE has occurred during the study period, this should also be recorded in the CRF. In addition, each study subject will be asked an open question about possible AEs at each clinic visit following initiation of treatment.

The following evaluations are to be done by the Investigator in connection with the AE:

- type of event
- seriousness
- degree of severity
- duration (start - end)
- action taken

	MGC Pharma Clinical Study Protocol	Protocol No.: MGC-009
		Version 02, 05 Sep 2021
		Page 56 of 76
A Phase IIb, double blind, placebo-controlled clinical study designed to evaluate the effect of CimetrA in patients diagnosed with COVID-19		CONFIDENTIAL

- likelihood of causality with study product
- outcome of the adverse event

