Biochemistry blood test: Sodium (Na), Potassium (K), Chloride (Cl), Creatinine, Glucose, Urea, Albumin, Calcium total, Alkaline Phosphatase (ALP), ALT, AST, Total Bilirubin, Direct Bilirubin, LDH, Total Protein, Uric Acid, CRP, and Lipid Profile (including Total Cholesterol, HDL, LDL, Triglycerides).

Hematology blood test: complete CBC.

D-Dimer test (coagulation): one tube for coagulation test

Inflammatory markers: the blood will be centrifuged and frozen according to the Lab manual, Local Lab.

Vital signs: blood pressure, pulse, weight, weight, body temperature (PO), saturation, respiratory rate.

VAS scale: will be performed by study staff member.

WHO Ordinal Score: will be completed by the study staff member based on patient status.

COVID-19-Related Symptoms assessment: will be completed by the study staff member based on patient status and answers.

COVID-19–Impact on Quality-of-Life Questionnaire: will be completed by the study staff member based on patient answers.

	MGC Pharma Clinical Study Protocol	Protocol No.: MGC-009
		Version 02, 05 Sep 2021
		Page 40 of 76
A Phase IIb, double blind, placebo-controlled clinical study designed to evaluate the effect of CimetrA in patients diagnosed with COVID-19		CONFIDENTIAL

POST- COVID-19 Functional Status Scale: will be completed by the study staff member based on patient answers.

Pregnancy test: women of childbearing potential must undergo a urine pregnancy test.

Physical examination: full examination by doctor.

** Measurements will be performed per institutional schedule by the hospital staff, not necessarily by the principal investigator or the sub-investigators.

PK parameters*: will be performed only on 14 patients that will agree to participate in the PK analysis (only for Brazil and South Africa).

The PK will be performed only for the first dose of drug, after patient received the first dose (5 puffs) the study staff need to follow the table below.

For each test, approximately 5 ml of blood will be drawn (equivalent to one teaspoon) total of 55 ml of blood will be drawn.

Table 6: List of time points for pharmacokinetic assessments

Study Visit Number 1	
Time point 0	Dosing (before the first dose of the drug)
Time Point 1	15 minutes post dose
Time Point 2	30 minutes post dose
Time point 3	45 minutes post dose
Time point 4	1 h post dose
Time point 5	1.5 h post dose
Time point 6	2 h post dose
Time point 7	4 h post dose
Time point 8	6 h post dose
Time point 9	8 h post dose

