Sample size and Power were calculated with the Power and Precision statistic program ver 4.1 and all statistical analyses and data presentations, including tabulations and listings, will be performed using the SPSS statistic program version 27.0 (or higher) software.

Randomization

Randomization tend to produce study groups comparable with respect to known and unknown risk factors, removed investigator bias in the allocation of participants and guarantees that statistical tests will have valid false positive error rates.

After a participant will meet the eligibility criteria, he/she will be randomly allocated (with a 1:1:1 ratio) to one of the following treatment groups based on a randomization scheme stratified by center.

The randomization scheme will be prepared by an independent statistician using statistic program for random number generator. The block size is set in ahead and study personnel will be blinded to the randomization block size.

Blinding

This is a double-blind study: neither the participants nor the investigators will be aware of arm allocation of each study participant.

Blindness is important to avoid bias. Monitoring and reporting of the success of blindness are important for the reader's confidence of the trial results. Groups should be marked by capital letter and blindness should maintain throughout the study.

Missing Data

Safety data should be collected from non-adherent/withdrawal participants to avoid possible bias.

	MGC Pharma Clinical Study Protocol	Protocol No.: MGC-009
		Version 02, 05 Sep 2021
		Page 62 of 76
A Phase IIb, double blind, placebo-controlled clinical study designed to evaluate the effect of Cimetra in patients diagnosed with COVID-19		CONFIDENTIAL

Prior to analyzing the data, extreme laboratory values should be checked. Missing values will be treated as ITT.

Multiple imputation for binary data will be used as the primary imputation method in the case of missing data for the primary efficacy endpoint.

Dropout/AE Imputation: A participant with no post baseline measurement or a participant withdrawn due to an adverse event or treatment intolerability will use last observation carried forward imputation methods.

Baseline Data

Baseline participant characteristics will be collected at screening. The specific baseline (“start of treatment”) endpoints and other symptoms will be collected prior to each treatment.

Significance Levels and Handling of Type I Error

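### The label fields, unequal spray volumes and volume-based compliance check in Sections 12.2 and 12.4 conflict with the double blind promised in Section 17

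*Protocol*

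**What the plan says.** All references are to the protocol.

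- **The promise.** Section 17 (Blinding) describes a double-blind trial in which neither participants nor investigators know any patient's arm. Section 12.2 adds: "Placebo will be administrated in the same way, and will be identical in its characteristics to the study drug in order to prevent bias".
- **The bottle.** Section 12.2: "CimetrA-1, CimetrA-2 and Placebo is supplied in a bottle containing 5 ml". The same section states: "Spray pump on product bottle enables dosing 0.2 ml of CimetrA-1 /0.14 ml of CimetrA-2 in each press". No volume per press is given for placebo.
- **The label.** Section 12.2 opens its list with "Study Product will be labeled with". The items are product name, dose, lot number, manufacturing date, protocol number, sponsor, instructions and an investigational-use statement. A kit, pack or randomization number is not among them.
- **Who handles it.** Under Section 12.4 a pharmacist or an authorised study team member looks after the supplies, which then pass to the Investigator before dosing. The Investigator or the pharmacist may dispense. Section 12.3 lets either of them record how much each subject used.
- **Compliance.** Section 12.4 on treatment compliance, assessed at every treatment-period visit: "It will be based on drug accountability (volume measure"), together with diary review.
- **Who scores.** Section 10.2.1: "WHO Ordinal Score: will be completed by the study staff member based on patient status". The COVID-19 symptoms score is also completed by a study staff member, from patient status and answers.

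**The concern.** A double blind needs supplies that do not disclose the arm to anyone whose judgement enters the outcome. Three features of Sections 12.2 and 12.4 work against that: label fields that identify product and dose, active presentations that differ in delivered volume, and a compliance measurement of that same volume. The Investigator, whom Section 17 counts among the blinded, receives the labelled bottle.

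Both primary efficacy endpoints in Section 9.1 are completed by study staff. The symptoms score relies on patient answers, and the step between WHO levels 1 and 2 turns on whether assistance is needed, so both leave room for judgement. Section 17 counts the study as successful if the omnibus null hypothesis is rejected. A scoring difference caused by knowledge of the arm could therefore be read as efficacy, and no later analysis would recover the lost blinding.

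**Working it through.** **Inputs.** Section 12.1: 5 puffs per dose, 2 doses a day, 4 doses in total, in each active arm. Section 12.2: 0.2 ml (CimetrA-1) and 0.14 ml (CimetrA-2) per press, 5 ml bottle in all arms.

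**Step 1: reproduce the stated volumes.** Volume per dose = puffs × ml per press.

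- Arm 1: 5 × 0.2 = 1.0 ml; per day 2 × 1.0 = 2.0 ml. Section 12.1: "Daily dosage is 2 ml which equal to 10 puffs from the study drug spray". Agrees.
- Arm 2: 5 × 0.14 = 0.7 ml; per day 2 × 0.7 = 1.4 ml. Section 12.1 gives the same figures.

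The unequal volumes are therefore stated consistently in two sections and are not a slip in one of them.

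**Step 2: what a volume check would show.** Assume one bottle per patient, exact fill, no priming loss and full compliance. None of these is stated.

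- Presses: 4 × 5 = 20.
- Arm 1: 20 × 0.2 = 4.0 ml used; 5 − 4.0 = 1.0 ml left.
- Arm 2: 20 × 0.14 = 2.8 ml used; 5 − 2.8 = 2.2 ml left.

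The two actives differ by 1.2 ml. Even without the one-bottle assumption, a five-puff dose differs by 0.3 ml (1.0 against 0.7 ml).

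**Step 3: where placebo falls.** A placebo with a 0.2 ml pump looks like CimetrA-1 and unlike CimetrA-2; with a 0.14 ml pump the reverse. With any other volume it matches neither. A single presentation cannot meet the requirement of identity with both.

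**Step 4: arm 2 dose figures.** Total = ml per dose × mg/ml × 4.

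| | Calculation from stated volume and concentration | Stated total |
|---|---|---|
| Arm 1 Curcuma | 1 × 7 × 4 = 28 mg | 28 mg |
| Arm 1 Boswellia | 1 × 15 × 4 = 60 mg | 60 mg |
| Arm 2 Curcuma | 0.7 × 4.9 × 4 = 13.72 mg | 19.6 mg |
| Arm 2 Boswellia | 0.7 × 10.5 × 4 = 29.4 mg | 42 mg |

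Arm 2 does not close. Its stated totals correspond to 19.6 / 4 = 4.9 mg and 42 / 4 = 10.5 mg per dose. Those amounts arise either if 4.9 and 10.5 are mg per dose rather than mg/ml, or if the dose volume is 1 ml. The protocol does not settle which, and the answer bears on whether the two actives need different volumes at all.

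**Step 5: illustration only.** The protocol contains nothing from which a scoring bias can be estimated. Suppose, purely as an assumption, that scorers shift both active arms by b points on the WHO scale relative to placebo, with no true effect and the planning SD of 1.5. The variance of the three means is 2b²/9, and the noncentrality is 240 × (2b²/9) / 1.5². From the noncentral F with 2 and 237 degrees of freedom, the nominal 5% omnibus test rejects in 6.8% of trials for b = 0.1, 12.7% for 0.2, 23.6% for 0.3 and 57.3% for 0.5. This shows how sensitive the test is to such a shift; it does not show that a shift would occur.

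**The case against.** The strongest defence is that the protocol lists label fields, not label text. Section 12.2 requires labelling under GMP and EU rules for trial drugs and a placebo made identical to prevent bias. Section 12.4 records a batch or pack number per subject, so some pack numbering exists. The dose field might be filled as five puffs, which is the same in both active arms. This stands to a degree: a reader might infer that the bottles will literally read CimetrA-1, CimetrA-2 or Placebo, and the protocol does not say so. But neither the general compliance sentence nor a number on an accountability form removes product name and dose from an explicit list, and the list has no coded identifier to replace them.

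A second defence is that the scorer need not be the person who sees the bottle. Section 10.2.1 names only a study staff member, and Section 12.4 gives final accountability to the monitor. Dosing ends on day 2, while post-baseline scoring falls on days 7, 14, 21 and 28, and much of the WHO scale is fixed by hospitalisation, oxygen mode, ventilation or death. This too stands in part: the protocol does not put the two roles in one person. It only fails to separate them, and what is learned on days 1 and 2 is still known on day 7.

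Third, volume does not by itself separate active from placebo. That is right for whichever active the placebo pump matches.

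Two stronger readings are tempting and are not supported. Section 17 says "Groups should be marked by capital letter and blindness should maintain throughout the study", and a reader might infer that decoding one patient exposes a whole arm of 80. No section puts the letter on a bottle or shows it to site staff, and the sentence fits masked group codes used at analysis equally well. A reader might also express a rater shift as a share of the planned treatment difference. The protocol gives f = 0.20 and SD 1.5 but no pairwise difference: two equal actives imply about 0.64, CimetrA-2 midway implies about 0.73. Any such shift would itself be assumed, so the ratio carries no evidential weight.

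**Conclusion.** The point holds as a conflict between sections. Followed as written, Sections 12.2 and 12.4 threaten the blind that Section 17 promises. The firmest elements are the product-name and dose fields with no coded identifier, and the 0.2 against 0.14 ml pumps combined with a placebo required to be identical to the study drug.

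In size, a five-puff dose differs by 0.3 ml between the actives. A used bottle would hold 1.0 against 2.2 ml, given one bottle per patient, exact fill, no priming loss and full compliance. That separates CimetrA-1 from CimetrA-2, and placebo from any active whose pump it does not match.

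The protocol does not establish that the blind will in fact be lost or that scorers will handle bottles, and it gives no basis for the amount of any resulting bias. Label content and pump design are protocol matters and would not normally be settled in a statistical analysis plan.

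**What to change.** 1. **Label (Section 12.2).** Replace product name, dose and any arm-identifying lot number with a unique kit number and wording such as *CimetrA or placebo*.
2. **Records (Sections 12.2 to 12.4).** Keep lot and certificate-of-analysis documents and volume accountability with the pharmacist or another designated product handler. State that this person does not score outcomes and that these records are withheld from those who do.
3. **Placebo (Section 12.2).** Match placebo to both active presentations, for example by supplying it in both pump volumes. State openly that this masks active against placebo but leaves CimetrA-1 distinguishable from CimetrA-2 by volume.
4. **Before pump volumes are settled,** reconcile the arm 2 volume, concentration and total-dose figures in Section 12.1.

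The cost is new label text, a kit list and two placebo presentations to manage, with no extra patients. Where a site uses a study team member rather than a pharmacist as product handler, someone else must score, which may need a staffing arrangement. The changes are cheap before supplies are labelled; blinding lost after enrolment starts cannot be restored.
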